7.0 Treatment Plan

We plan to study 2 different patient groups (lower risk MDS [defined as low and int-1 by IPSS] and higher risk [defined as int-2 and high risk by IPSS]) with 2 cohorts each. Each cohort will be composed of N=20 patients. Accrual to cohort will be sequential in each patient group. Accrual will be parallel for each patient group.

All treatments can vary +/- 3 days.

1. Lower Risk MDS cohorts (Low and Int-1):

- Cohort 1: Lirilumab single agent Q4 wks.
- Cohort 2: Lirilumab Q4 weeks+ Nivolumab, Q2 wks X 9 cycles then both Q4 wks.

2. Higher Risk MDS cohorts (Int-2 and High):

- Cohort 3: 5-azacitidine IV, D1-7 of 28 day cycle, in combination with Lirilumab IV on D7

- Cohort 4: 5-azacitidine IV, D1-7 of 28 day cycle, in combination with Lirilumab IV Day 7 and Nivolumab IV D7 & D21 X 9 cycles then D7 only on Cycle 10 +

Specific cohorts can be closed based on ongoing experience with this trial or other relevant information.

Patients will receive study drug(s) according to the following treatment plan. Individual minor variations in the initiation of therapy, are acceptable as indicated by patient condition and physician judgment. These variations should be documented in the patient's medical record.

Dosing calculations for Nivolumab and 5-Azacitidine will be based actual body weight.

Single agent:

Lirilumab: Patient will receive lirilumab 3 mg/kg IV over approximately 60 minutes every 4 weeks. One cycle is defined as 4 weeks.

Combination:

Lirilumab and Nivolumab: Patient will receive Nivolumab 3 mg/kg IV over approximately 60 minutes every 2 weeks for 9 cycles. Lirilumab will be administered at 3 mg/kg IV over approximately 60 minutes once every 4 weeks. One cycle will be defined as 4 weeks.

Azacitidine+ lirilumab: Azacitidine 75 mg/m² IV daily x 7 days and lirilumab 3 mg/kg IV over approximately 60 minutes on day 7. A cycle will be considered 4 weeks.

Azacitidine+ lirilumab + Nivolumab: Azacitidine 75 mg/m² IV daily x 7 days followed on day 7 by nivolumab and lirilumab and nivolumab also on day 21. A cycle will be

considered 4 weeks. Doses of nivolumab and lirilumab are 3 mg/kg IV each over approximately 60 minutes.

Dose Adjustments

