Based on the adverse effect profiles of the 3 agents, the following dose adjustments are recommended. Hematological toxicities will be attributed primarily to Azacitidine and preferentially will be dose reduced (Table 1). Specific non-hematological toxicities will be attributed primarily to NIVOLUMAB OR LIRILUMAB. No dose reductions of these two agents are allowed, see below.

Table 1: Dose Adjustments for Grade 3 – 4 Hematological Toxicity

	Azacitidine IV (x 7 days)
Level – 1	50 mg/m ² /day
Level – 2	25 mg/m ² /day

Nivolumab and Lirilumab Dose Modification

Nivolumab/ Lirilumab Dose reductions or dose escalations are not permitted.

Dose Delay Criteria:

Because of the potential for clinically meaningful nivolumab-related AEs requiring early recognition and prompt intervention, management algorithms have been developed for suspected AEs of selected categories.

Dose delay criteria apply for all drug-related adverse events

Nivolumab & Lirilumab administration should be delayed for the following:

- Any Grade \geq 2 non-skin, drug-related AE, with the following exceptions:
 - Grade 2 drug-related fatigue or laboratory abnormalities do not require a treatment delay
 - However, dose delays should occur for the following laboratory

abnormalities:

- G2 Creatinine, or
- G2 ALT, AST or total bilirubin
- Any Grade 3 skin, drug-related AE
- Any Grade 3 drug-related laboratory abnormality, with the following exceptions for lymphopenia, leukopenia, AST, ALT, total bilirubin, or asymptomatic amylase or lipase:
 - Grade 3 lymphopenia or leukopenia does not require dose delay.
 - Grade 3 AST, ALT or total bilirubin requires permanent discontinuation of nivolumab
- Any AE, laboratory abnormality, or intercurrent illness which, in the judgment of the investigator, warrants delaying the dose of study medication.

Criteria to Resume Treatment:

Subjects may resume treatment with study drug when the drug-related AE(s) resolve to Grade ≤ 1 or baseline value, with the following exceptions:

- Subjects may resume treatment in the presence of Grade 2 fatigue
- Subjects who have not experienced a Grade 3 drug-related skin AE may resume treatment in the presence of Grade 2 skin toxicity
- Drug-related pulmonary toxicity, diarrhea, or colitis, must have resolved to baseline before treatment is resumed
- Drug-related endocrinopathies adequately controlled with only physiologic hormone replacement may resume treatment

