If the criteria to resume treatment are met, the subject should restart treatment at the next scheduled timepoint per protocol. However, if the treatment is delayed past the next scheduled timepoint per protocol, the next scheduled timepoint will be delayed until dosing resumes.

If treatment is delayed > 6 weeks, the subject must be permanently discontinued from study therapy, except as specified in discontinuation section.

Management Algorithms:

Immuno-oncology (I-O) agents are associated with AEs that can differ in severity and duration than AEs caused by other therapeutic classes. Nivolumab & Lirilumab are considered immuno-oncology agents in this protocol. Early recognition and management of AEs associated with immuno-oncology agents may mitigate severe toxicity. Management algorithms have been developed to assist investigators in assessing and managing the following groups of AEs:

Gastrointestinal, Renal, Pulmonary, Hepatic, Endocrinopathies, Skin, Neurological.

For subjects expected to require more than 4 weeks of corticosteroids or other immunosuppressants to manage an AE, consider recommendations provided in the algorithms. The guidance provided in these algorithms should not replace the Investigator's medical judgment but should complement it.

Discontinuation Criteria:

Treatment should be permanently discontinued for the following:

- Any Grade 2 drug-related uveitis or eye pain or blurred vision that does not respond to topical therapy and does not improve to Grade 1 severity within the re-treatment period OR requires systemic treatment

- Any Grade 3 non-skin, drug-related adverse event lasting > 7 days, with the following exceptions for drug-related laboratory abnormalities, uveitis, pneumonitis, bronchospasm, diarrhea, colitis, neurologic adverse event, hypersensitivity reactions, and infusion reactions:
 - Grade 3 drug-related uveitis, pneumonitis, bronchospasm, diarrhea, colitis, neurologic adverse event, hypersensitivity reaction, or infusion reaction **of any duration** requires discontinuation

 - Grade 3 drug-related laboratory abnormalities do not require treatment

discontinuation except those noted below:

- Grade 3 drug-related thrombocytopenia > 7 days or associated with bleeding requires discontinuation
- Grade 3 drug-related ALT, AST, or total bilirubin require discontinuation
- Any Grade 4 drug-related adverse event or laboratory abnormality, except for the following events which do not require discontinuation:

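### In Cohorts 3 and 4 the plan does not say whether a severe cytopenia means reducing azacitidine or permanently stopping treatment; separately, AST, amylase and lipase drive dosing rules but are not in the on-treatment panel

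*Combined protocol and SAP*

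**What the plan says.** **Cytopenias.** Section 7.0, Dose Adjustments, states: "Hematological toxicities will be attributed primarily to Azacitidine and preferentially will be dose reduced (Table 1"). That table covers grade 3 and 4 events and steps azacitidine down to 50 and then 25 mg/m² per day. The next sentence reads "Specific non-hematological toxicities will be attributed primarily to NIVOLUMAB OR LIRILUMAB", and dose reductions of the two antibodies are not allowed.

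**Discontinuation.** The heading "Nivolumab and Lirilumab Dose Modification" follows, and then the delay, resumption and discontinuation rules. The delay list opens with "Dose delay criteria apply for all drug-related adverse events" and then names nivolumab and lirilumab as the drugs to be delayed. The Discontinuation Criteria open by saying only that treatment stops permanently. Their triggers include:

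- "Any Grade 4 drug-related adverse event or laboratory abnormality, except for the following events which do not require discontinuation", where the exceptions are certain isolated amylase or lipase findings and certain electrolyte findings;
- grade 3 drug-related thrombocytopenia that lasts beyond 7 days or comes with bleeding;
- grade 3 drug-related ALT, AST or total bilirubin.

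The last bullet, on investigator judgment, refers to continued dosing with nivolumab.

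**Liver tests in the delay list.** "Grade 3 AST, ALT or total bilirubin requires permanent discontinuation of nivolumab".

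**Laboratory schedule.** Section 9.0 measures AST, amylase and lipase before treatment. The panel in Section 10.0 does not list them. That panel is weekly in the first course, then once per course at the physician's discretion.

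**The concern.** Two problems share these pages.

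First, one event in Cohorts 3 and 4 can fall under two rules that lead to different actions. A grade 4 neutropenia, or a grade 3 thrombocytopenia lasting beyond 7 days, calls for less azacitidine under one rule and for permanent discontinuation under the other. Two physicians could act differently on the same blood count. The literal reading would also permanently end the antibodies under study for an event that the plan elsewhere expects to manage by lowering azacitidine. Section 15.0 keeps every patient who received any dose in the efficacy analysis and assesses response after 6 cycles, so a patient whose antibodies were stopped early would still count in the response rate.

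Second, some delay and discontinuation rules depend on results that nobody is scheduled to obtain. An isolated grade 3 or 4 AST, amylase or lipase event could go unseen. It would then trigger no action and be missing from the toxicity counts, in a trial whose primary objective is safety.

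**Working it through.** The plan gives no figure to reproduce here. The check sets the texts side by side and makes two counts.

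**1. Events covered twice in Cohorts 3 and 4**

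| Event, if judged drug-related | Azacitidine rule (Section 7.0, Table 1) | Discontinuation Criteria |
|---|---|---|
| Grade 4 neutropenia, leukopenia, anemia or thrombocytopenia | Reduce azacitidine | Stop; no cytopenia is among the grade 4 exceptions |
| Grade 3 thrombocytopenia beyond 7 days or with bleeding | Reduce azacitidine | Stop |
| Grade 3 AST, ALT or bilirubin | Not covered | Delay list: stop nivolumab. Discontinuation list: stop treatment, drug not named |

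**2. What the wording allows for a grade 4 cytopenia.** Three readings are open, each with a different outcome:

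- *Treatment means the whole regimen.* Azacitidine stops with the antibodies. No dose is left to reduce, so the two rules cannot both be followed.
- *Treatment means the antibodies, and drug-related means related to any study drug.* Both rules can be carried out, but every severe drug-related cytopenia ends the antibodies.
- *Treatment means the antibodies, and drug-related means antibody-related.* A cytopenia attributed to azacitidine leads only to a lower azacitidine dose.

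No sentence chooses among these. Section 12.0 grades attribution against the study treatment, not against each agent. The words primarily and preferentially in the azacitidine rule are not exclusive.

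**3. Scope of the overlap.** Cohorts 3 and 4 have 20 patients each: 2 × 20 = 40 of 80 planned. This counts patients to whom the wording applies, not patients who would have an event. Section 8.3 reports thrombocytopenia in 65.5% and neutropenia in 32.3% on azacitidine, without a split by grade. The documents give no grade 4 rate, so an expected number cannot be derived.

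**4. Laboratory tests**

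- Baseline chemistry (Section 9.0): creatinine, total bilirubin, ALT, AST, amylase, lipase, TSH = 7 tests.
- Repeated on treatment (Section 10.0): creatinine, total bilirubin, SGPT (which is ALT), TSH = 4 tests.
- Not repeated: 7 − 4 = 3 tests, namely AST, amylase and lipase.

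All three appear in the Section 7.0 rules. Grade 2 AST calls for a delay and grade 3 AST for a permanent stop. A grade 4 amylase or lipase value escapes discontinuation only if it is isolated, without signs of pancreatitis, and falls below grade 4 within 1 week. No scheduled test can show that. Section 8.3 does require a blood count before each dosing cycle as a minimum, but only because of azacitidine, and it does not cover chemistry.

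**5. Stopping rule.** The toxicity rule in Section 15.0 counts therapy-related non-hematological grade 3/4 events. Cytopenias do not enter it, so item 2 leaves it untouched. An undetected grade 3/4 AST, amylase or lipase event would be missing from the count, but the boundaries themselves (4 of 5, 7 of 10, 9 of 15) are unaffected.

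**The case against.** The best defense is structure. Azacitidine and its reduction table come first. The antibody heading follows, then delay, resumption, the immuno-oncology algorithms and discontinuation. Hematological toxicity has by then been assigned mainly to azacitidine, so a cytopenia so attributed is not naturally an antibody event. The blood-count bullets are needed for Cohorts 1 and 2 in any case. The azacitidine adjustments are introduced as recommended, and a cytopenia caused by the MDS itself is not drug-related at all. Heading levels were also lost when the PDF was read, so some of the missing scope may be an artefact.

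Much of this stands: an antibody-only scope is a natural reading. But it is inferred. Nothing limits the blood-count bullets to Cohorts 1 and 2, no precedence is stated, and whether azacitidine may continue is not addressed on any reading.

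On the laboratory tests, the reply is that ALT and bilirubin are scheduled and trigger the same liver rules, and that symptomatic pancreatitis would prompt testing. This is right and keeps the gap small. It does not cover an isolated AST rise or a silent amylase or lipase rise.

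Three stronger inferences should be resisted:

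- *That the discontinuation rules name no drug.* The last bullet names nivolumab, and the preceding heading names both antibodies.
- *That Cohorts 1 and 3 have no instruction because they receive no nivolumab* ("Cohort 1: Lirilumab single agent Q4 wks"; "Cohort 3: 5-azacitidine IV, D1-7 of 28 day cycle, in combination with Lirilumab IV on D7"). The general stop of treatment applies to them. So do items 4 and 5 of the reasons for ending treatment in Section 7.0, on patient condition and unacceptable toxicity.
- *That Section 8.1.5 contradicts Section 7.0 on infusion reactions.* Section 8.1.5 deals only with nivolumab-related reactions, so it is expected to name nivolumab.

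**Conclusion.** The point holds and is minor. In Cohorts 3 and 4 the plan has two rules for grade 4 cytopenias and for prolonged or bleeding grade 3 thrombocytopenia, and no statement of which governs or whether azacitidine also stops. The grade 3 liver rule is worded in two ways. Three laboratory tests that the rules rely on are not scheduled during treatment, and the panel they would belong to is discretionary after course 1.

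The scope is 40 of 80 planned patients for the cytopenia overlap and 3 of 7 baseline chemistry tests for the monitoring gap. How many patients would be affected cannot be computed from the documents.

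A reader might infer that patients will lose their antibodies wrongly. The documents do not show that: it depends on how physicians read the rules, and a precautionary antibody stop may be what the sponsor intends. Nor do they support saying that the trial's stopping boundaries are compromised. The conclusion assumes that no other text, such as the management algorithms that Section 7.0 mentions, settles the precedence.

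**What to change.** 1. Add AST, amylase and lipase to the Section 10.0 panel, and make the once-per-course blood count and chemistry mandatory. The cost is three extra assays per visit on blood already drawn.
2. In the Discontinuation Criteria, state which drug or drugs stop and whether azacitidine may continue. Make the two grade 3 AST/ALT/bilirubin statements agree by naming nivolumab, lirilumab or both.
3. State which rule governs grade 4 cytopenias and the listed grade 3 thrombocytopenia in Cohorts 3 and 4. This is a clinical choice for the sponsor. One option is azacitidine reduction when the event is attributed to azacitidine, keeping the discontinuation bullets for events attributed to an antibody. The other is a precautionary antibody stop, said in one sentence with the drugs named.

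Items 2 and 3 cost only amendment wording. The first option in item 3 relies on the investigator's attribution, so an antibody-caused cytopenia could be wrongly assigned to azacitidine. Keeping the bullets for antibody-attributed events limits that risk but does not remove it.

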8.0 Study Medications

For treatment visits where both Lirilumab and Nivolumab are administered, Nivolumab will be administered first followed by Lirilumab within 30 minutes after completion of the Nivolumab.

8.1 Nivolumab (Anti-PD1)

Nivolumab is a fully human, IgG4 (kappa) isotype, monoclonal antibody that binds PD-1. Nivolumab will be supplied in vials of 100 mg (10 mg/mL) and packaged in an open-label fashion. Ten nivolumab vials (each 10 mL) will be packaged within a carton. The vials are not subject specific although there will be specific vial assignments by subject distributed by the Pharmacy in order to track drug usage and re-supply.

PRODUCT INFORMATION TABLE:

Product Description:(Other names = MDX-1106, ONO-4538, anti-PD-1)

Product Description and Dosage Form	Potency	Primary Packaging (Volume)/ Label Type	Secondary Packaging (Qty)/Label Type	Appearance	Storage Conditions (per label)
-------------------------------------	---------	--	--------------------------------------	------------	--------------------------------

Nivolumab (BMS-936558-01)* Injection drug product is a sterile, non-pyrogenic, single-use, isotonic aqueous solution formulated at 10 mg/mL	100 mg/Vial (10 mg/mL)	Carton of 5 or 10 vials	10-cc Type 1 flint glass vials stoppered with butyl stoppers and sealed with aluminum seals.	Clear to opalescent, colorless to pale yellow liquid. May contain particles	BMS-936558-01 Injection must be stored at 2 to 8 degrees C (36 to 46 degrees F) and protected from light and freezing
--	---------------------------	----------------------------	---	---	---

*Nivolumab may be labeled as BMS-936558-01 Solution for Injection

8.1.1 Dose Calculation of nivolumab

Total dose should be calculated as in the following example:

Subject's actual body weight in kg x 3 mg = total dose in mg

Therefore, a subject weighing 70 kg who is to receive a dose of 3 mg/kg would be administered 210 mg of nivolumab (70 kg x 3 mg/kg = 210 mg).

8.1.2 Preparation and Dispensing of Nivolumab

The product storage manager should ensure that the study drug is stored in accordance with the environmental conditions (temperature, light, and humidity) as determined by the Investigator Brochure. If concerns regarding the quality or appearance of the study drug arise, do not dispense the study drug and contact the sponsor immediately.

Investigational product documentation must be maintained that includes all processes required to ensure drug is accurately administered. This includes documentation of drug storage, administration and, as applicable, storage temperatures, reconstitution, and use of required processes (e.g. required diluents, administration sets).

Nivolumab vials must be stored at a temperature of 2°C to 8°C and should be protected from light. If stored in a glass front refrigerator, vials should be stored in

the carton. Recommended safety measures for preparation and handling of nivolumab include laboratory coats and gloves.

For details on prepared drug storage and use time of nivolumab under room temperature/light and refrigeration, please refer to the Investigator Brochure section for “Recommended Storage and Use Conditions”. Care must be taken to assure sterility of the prepared solution as the product does not contain any antimicrobial preservative or bacteriostatic agent. No incompatibilities between nivolumab and polyolefin bags have been observed.

Nivolumab is to be administered as a 60 minute IV infusion, using a volumetric pump with a 0.2/0.22 micron in-line filter at the protocol-specified dose. The drug can be diluted with 0.9% normal saline for delivery but the total drug concentration of the solution cannot be below 0.35 mg/ml. It is not to be administered as an IV push or bolus injection. At the end of the infusion, flush the line with a sufficient quantity of normal saline.

8.1.3 Administration of nivolumab

Patients will receive nivolumab as a 60 minute IV. Dosing calculations should be based on the body weight assessed at the start of each cycle as described above. All doses should be rounded to the nearest milligram. The screening body weight may be used for dosing of cycle 1.

Patients may be dosed no less than 12 days from the previous dose of drug.

The dosing calculations should be based on the actual body weight. If the subject’s weight on the day of dosing differs by > 10% from the weight used to calculate the original dose, the dose must be recalculated. All doses should be rounded to the nearest milligram. There will be no dose modifications allowed

8.1.4 Patient Monitoring During Infusion

Patient vital signs should be monitored prior to dosing, about 15 minutes after initiation of the infusion (then every 15-20 minutes as indicated), at 60 and 120 minutes after completion of the infusion, or longer if indicated, until the vital signs normalize or return to baseline. For subsequent infusions, vital signs should be collected prior to dosing, every 30 minutes during dosing, and 1 hour post dosing. All vital sign times will be +/- 10 mins.

8.1.5 Treatment of nivolumab Related Infusion Reactions

Since nivolumab contains only human immunoglobulin protein sequences, it is unlikely to be immunogenic and induce infusion or hypersensitivity reactions. However, if such a reaction were to occur, it might manifest with fever, chills, rigors, headache, rash, pruritis, arthralgias, hypo- or hypertension, bronchospasm, or other symptoms. All Grade 3 or 4 infusion reactions should be reported within 24 hours to the BMS Medical Monitor and reported as an SAE if criteria are met. Infusion reactions should be graded according to NCI CTCAE (version 4.0) guidelines.

Treatment recommendations for nivolumab related infusion reactions are provided below and may be modified based on MD Anderson treatment standards and guidelines, as appropriate:

For Grade 1 symptoms (Mild reaction; infusion interruption not indicated; intervention not indicated): Remain at bedside and monitor subject until recovery from symptoms. The following prophylactic premedications are recommended for future infusions: diphenhydramine 50 mg (or equivalent) and/or acetaminophen 325 to 1000 mg at least 30 minutes before additional nivolumab administrations.

For Grade 2 symptoms (Moderate reaction requires therapy or infusion interruption but responds promptly to symptomatic treatment [e.g. antihistamines,

non-steroidal anti-inflammatory drugs, narcotics, corticosteroids, bronchodilators, IV fluids]; prophylactic medications indicated for ≤ 24 hours):

Stop the nivolumab infusion, begin an IV infusion of normal saline, and treat the subject with diphenhydramine 50 mg IV (or equivalent) and/or acetaminophen 325 to 1000 mg; remain at bedside and monitor subject until resolution of symptoms. Corticosteroid or bronchodilator therapy may also be administered as appropriate. If the infusion is interrupted, then restart the infusion at 50% of the original infusion rate when symptoms resolve; if no further complications ensue after 30 minutes, the rate may be increased to 100% of the original infusion rate. Monitor subject closely. If symptoms recur then no further nivolumab will be administered at that visit. Administer diphenhydramine 50 mg IV, and remain at bedside and monitor the subject until resolution of symptoms. The amount of study drug infused must be recorded on the case report form (CRF). The following prophylactic premedications are recommended for future infusions: diphenhydramine 50 mg (or equivalent) and/or acetaminophen 325 to 1000 mg should be administered at least 30 minutes before additional nivolumab administrations. If necessary, corticosteroids (recommended dose: up to 25 mg of IV hydrocortisone or equivalent) may be used.

For Grade 3 or Grade 4 symptoms [Severe reaction, Grade 3: prolonged (i.e. not rapidly responsive to symptomatic medication and/or brief interruption of infusion); recurrence of symptoms following initial improvement; hospitalization indicated for other clinical sequelae (e.g. renal impairment, pulmonary infiltrates), Grade 4: life- threatening; pressor or ventilatory support indicated]:

Immediately discontinue infusion of nivolumab. Begin an IV infusion of normal saline, and treat the subject as follows: Recommend bronchodilators, epinephrine 0.2 to 1 mg of a 1:1,000 solution for subcutaneous administration or 0.1 to 0.25 mg of a 1:10,000 solution injected slowly for IV administration, and/or

diphenhydramine 50 mg IV with methylprednisolone 100 mg IV (or equivalent), as needed. Subject should be monitored until the investigator is comfortable that the symptoms will not recur. Nivolumab will be permanently discontinued. Institutional guidelines will be followed for the treatment of anaphylaxis. Remain at bedside and monitor subject until recovery from symptoms. In the case of late-occurring hypersensitivity symptoms (e.g. appearance of a localized or generalized pruritus within 1 week after treatment), symptomatic treatment may be given (e.g. oral antihistamine or corticosteroids).

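### Section 8.1.5 tells staff only to withhold nivolumab for the visit when infusion symptoms recur, without sending them to the Grade 3 steps that the protocol's own grading requires

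*Combined protocol and SAP*

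**What the plan says.** Section 8.1.5 sets out how nivolumab infusion reactions are handled, by grade. Its opening paragraph requires grading by NCI CTCAE version 4.0 and adds: "All Grade 3 or 4 infusion reactions should be reported within 24 hours to the BMS Medical Monitor". It describes the treatment steps as recommendations that "may be modified based on MD Anderson treatment standards and guidelines, as appropriate".

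For Grade 2, staff stop the infusion, treat the symptoms, and restart at half the original rate once symptoms have resolved. The next contingency reads: "If symptoms recur then no further nivolumab will be administered at that visit". Staff are then told to give intravenous diphenhydramine and to monitor at the bedside. After a sentence on recording the amount infused, the paragraph continues: "The following prophylactic premedications are recommended for future infusions".

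The next paragraph defines Grade 3 and lists, as one of its criteria, "recurrence of symptoms following initial improvement". For Grade 3 or 4 the instruction is: "Nivolumab will be permanently discontinued".

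The Discontinuation Criteria in Section 7.0 open with "Treatment should be permanently discontinued for the following". They include, whatever its duration, "Grade 3 drug-related uveitis, pneumonitis, bronchospasm, diarrhea, colitis, neurologic adverse event, hypersensitivity reaction, or infusion reaction".

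**The concern.** One bedside event is covered in two places. Staff working through the Grade 2 paragraph meet what looks like a complete instruction for recurrence: withhold for this visit, give an antihistamine, monitor. They then read about premedication for the next infusion. Nothing there tells them that the event now meets the Grade 3 definition or sends them to the following paragraph.

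Three things are at stake for such a patient:

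- re-exposure to a drug that the protocol says must be stopped for good;
- a missed 24-hour report to the company's medical monitor;
- acute treatment limited to the Grade 2 measures.

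Safety is the trial's primary objective, and the gap bears on the two cohorts that receive nivolumab (Cohorts 2 and 4).

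**Working it through.** No arithmetic applies, and the plan states no figure to reproduce. The check sets the instructions side by side.

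1. **Does the event meet the Grade 3 wording?** In the Grade 2 pathway the infusion restarts only after symptoms have resolved. A return of symptoms after that is recurrence after improvement. In the Grade 3 definition this criterion is set off by semicolons from prolonged reaction and from hospitalization, so it stands alone. The Grade 2 definition rests on a prompt response to treatment and does not mention recurrence. By the printed definitions the event is Grade 3.

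2. **What does each place require?**

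| | Grade 2 paragraph, recurrence | Grade 3/4 steps |
|---|---|---|
| Nivolumab | Withheld for that visit | Permanently stopped (8.1.5 and 7.0) |
| Later infusions | Premedication recommended, no exclusion | None |
| Acute treatment | Diphenhydramine | Bronchodilators, epinephrine, and/or diphenhydramine with methylprednisolone, as needed |
| Reporting | Not mentioned | Within 24 hours |

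3. **Can both be obeyed?** Literally, yes. Staff can withhold the rest of today's dose and then discontinue permanently. Neither text forbids the other.

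4. **What does the Grade 2 text convey on its own?** If recurrence always meant permanent discontinuation, limiting the instruction to that visit would serve no purpose. The premedication sentence follows in the same paragraph with no limit to patients whose symptoms stayed away. Together they imply that a later dose is allowed.

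5. **What follows if the event is left as Grade 2?** The Criteria to Resume Treatment in Section 7.0 let dosing restart once a drug-related event is back to Grade 1 or lower, or to baseline. What remains is the investigator-judgment stop at the end of the Discontinuation Criteria.

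6. **Does the flexibility clause settle it?** No. It lets institutional standards modify the recommendations in 8.1.5, but it does not say which instruction governs recurrence. The Discontinuation Criteria in Section 7.0 carry no such clause.

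7. **Can the frequency be estimated?** No. The documents give no recurrence rate. Section 3.0 reports infusion-related reactions in 2 of 306 subjects (0.7%) in its account of treatment-related discontinuations on nivolumab monotherapy. Those are discontinuations, not recurrences after a restart, and the figure bounds recurrence in neither direction.

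**The case against.** The strongest reply is that the protocol already resolves the matter. Section 8.1.5 requires CTCAE grading, Section 12.0 records the maximum grade per cycle, and the Grade 3 definition stands directly below the Grade 2 steps. Once the event is graded as told, Sections 7.0 and 8.1.5 both require a permanent stop. On this view the defect is a missing cross-reference. Most of that stands, and it is why the point is one of misdirection. It does not remove the point, because the Grade 2 paragraph gives an apparently finished instruction for an event that is no longer Grade 2.

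The reporting concern is also narrower than it first looks. Section 12.0 separately requires every serious adverse event to reach the company within 24 hours, so only a non-serious recurrence could go unreported.

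Four stronger readings are tempting but unsupported:

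- A reader might infer that the protocol orders re-dosing, or that the two instructions exclude each other. It does neither. It leaves re-dosing open.
- A reader might infer that recurrences would go unnoticed because scheduled toxicity assessments fall to once per course after the first. Those visits are not how an infusion reaction is found. Section 8.1.4 requires vital-sign monitoring around and during the infusion, and the Grade 2 steps keep staff at the bedside.
- A reader might infer a distorted toxicity stopping rule in Section 15.0, since a related Grade 3 event counts there. That would need the event to be misgraded despite the CTCAE instruction, and nothing in the documents shows that it would be.
- A reader might infer a conflict of scope, because Section 7.0 speaks of treatment and 8.1.5 of nivolumab. The Section 7.0 criteria fall under the heading on nivolumab and lirilumab dose modification, and azacitidine has its own adjustment table. The documents do not support reading the criteria as stopping all study treatment, and 8.1.5 names nivolumab because it is the nivolumab section.

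**Conclusion.** The point holds as a patient-safety clarification. Symptoms that recur after a restarted nivolumab infusion meet the protocol's own Grade 3 definition, which carries permanent discontinuation and a 24-hour report. The Grade 2 paragraph handles the same event as a matter for one visit, implies that later premedicated dosing is allowed, and does not point to the Grade 3/4 steps.

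Harm requires staff to follow the Grade 2 paragraph and leave the event at that grade. The event is probably rare, but that is a judgment, since its frequency cannot be estimated from the documents. For an affected patient the consequence is re-exposure to a drug that should have been stopped. No effect on any endpoint or analysis is claimed. The conclusion rests on the printed definitions, with recurrence read as a Grade 3 criterion in its own right.

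**What to change.** Make two edits in the Grade 2 paragraph of Section 8.1.5.

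1. Replace the recurrence sentence and the diphenhydramine sentence that follows it with: *If symptoms recur after restart, stop the infusion, grade the event as Grade 3, and follow the Grade 3/4 instructions below (treatment as needed), including permanent discontinuation of nivolumab and the 24-hour report.* Both sentences must go. If the second stayed, a Grade 2 treatment step would follow a Grade 3 instruction. Bedside monitoring is not lost, because the Grade 3/4 paragraph has its own instruction for it.

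2. Begin the premedication sentence with: *For patients whose symptoms did not recur*.

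The cost is a few lines of text, with no added data or patients. The downside is that a rare patient with a mild recurrence loses later nivolumab, which Sections 7.0 and 8.1.5 already require. Keeping treatment as needed in the new sentence avoids implying that every mild recurrence calls for the full set of Grade 3/4 drugs.
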